During the screening or baseline study visit, all participants will receive training to appropriately check blood pressure at home using study-issued home blood pressure monitors. A baseline chemistry panel and assessment of albuminuria will be ordered, if not completed clinically within 3 months of the study visit.

Both groups will complete an initial study visit with the study team and physician and complete a 24-hour ABPM session. The ABPM session can be done prior to training for the intervention participants.

4. Random allocation and blinding. Randomization will be 1:1 intervention/control. Randomization will be done by a central system, stratified by degree of hypertension at initial visit (> 160 systolic or below) and block-randomized by clinical sites using the centralized randomization tool through the Health Services Research Center data servers. The study participants and personnel will be unblinded. The research assistant in charge of checking blood pressures at the initial, 6-month, and 12-month visits may be aware of treatment allocation but will use standard procedures and an automated Omron cuff, using the SPRINT study blood pressure measurement protocol (5 minutes of quiet rest followed by 3 automated blood pressures at one-minute intervals, averaging last 2 to determine in-clinic BP), to ascertain blood pressures to avoid digit preference and bias.

5. Follow-up study visits: Participants in both randomization arms will then return for 6-month and 12-month study visits at which times blood pressure will be checked by a research assistant, and participants will complete questionnaires similar to those obtained at baseline, blood and urine studies for kidney function and albuminuria (as part of routine clinical care) at 12-month visit, and repeat ABPM at both 6 and 12-month visits.

6. Usual care and intervention protocols. Both groups will be issued a home blood pressure cuff with data recording capabilities identical to that in the active arm of the study, (Microlife BP, Microlife USA Inc), will meet the study physician and have questions answered, and will be instructed to record and share results with their primary care physician at routine clinic visits. The patient's and provider's willingness to titrate to a clinical goal of 130/80 (home goal of 120/75) will be confirmed.

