 Primary care 'burnout' from study burdens – confusion about response to participants in a blood pressure study

Approach: repeated and patient education, for both physicians and PACT team

Chapter 6. Procedures for Inactive/Lost/Refused Participants and Missed Visits

During the course of the study, we may find that certain participants become disinterested or frustrated. Participants in the active arm of the study may fail that arm (because of increasing meds above study titration plan, failure to follow protocol, etc) but should stay in the study for follow up purposes in intention to treat fashion.

Potential status options for a participant are:

- Active status a participant is considered to be active if following the assigned randomized treatment and in contact with the study.
- Inactive status a participant is considered to be inactive if he or she is no longer selfmonitoring/self-managing for any reason (but is still in contact with study).
- Lost status a participant is considered to be lost-to-follow-up if he/she has
 missed more than a follow-up visit, cannot be contacted by any ordinary
 means (e.g., home phone, cell phone, mail, email, fax, etc.), clinic staff do not know the
 participant's whereabouts, and alternative contacts either do not know where the
 participant is or cannot be contacted themselves.
- Refused status a participant is considered to be refused if he/she has withdrawn consent to participate in the study and refuses further contact for any reason.

To the greatest extent possible, we will attempt to complete follow-up visits for participants who are either active or inactive and to contact lost participants.

Chapter 7. Ascertainment of Study Outcomes

Blood pressure will be measured in the primary care clinic at the start of the study. We will use the clinically measured blood pressure as the blood pressure used for eligibility criteria, since primary care physicians may act on this blood pressure prior to the patient enrolling in the study.

Study clinic blood pressure will also be used to verify primary care clinic measurements and ensure that blood pressure is at least 130 systolic at baseline.

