At the baseline, six-month, and twelve-month visits, the blood pressure will be measured by a research protocol (3 measurements with interval pauses as above). The blood pressure from the research study visit on the day of randomization will serve as the baseline study visit for this trial. The outcome blood pressure will be the similarly measured (research protocol) blood pressure at the 12 month study visit.

ABPM set-up will be done according to our previously used Spacelabs protocols from SPRINT study.

All study instruments will be administered by research staff in-person with patients at the baseline, 6 and 12 month visits.

Chapter 8. Safety Monitoring and Reporting

The main clinical adverse events that will be monitored during this trial are those related to overor under-treatment of blood pressure. These were not different from usual care during the two studies of similar interventions in the UK, and only 3% of those in the intervention group deviated from self-titration protocols in those studies. Nevertheless, we plan to actively monitor for these issues by scheduled chart review for clinical or ER visits, hospitalizations, and potentially study-related serious adverse events (e.g. syncope, hypertensive urgency, stroke, MI, death). Other adverse events potentially related to the study will also be collected (e.g. medication side effects, abnormal laboratory findings including sodium < 130 or potassium <3 (for those on thiazide); potassium >6 for those on ACE; creatinine 50% higher than baseline).

We have assembled a DSMB for this study given the potential risks of self-management of blood pressure. This will consist of experienced nephrologist-epidemiologists and a general internist, all working in the VA system. Assisted by the study statistician they will review AEs and BP data in both groups at the point where each group of 100 participants have reached the six-month time point.

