2. Data analytic plan. Preliminary analyses will begin with an examination of the distribution of variables to assess their characteristics (means, standard deviations, medians, outliers), to provide descriptive statistics of the study population, and to allow assessment of randomization. Continuous measures will be tested for normality and non-normally distributed variables will be transformed to meet the normal distribution assumption for linear models. Randomization will be tested by performing a series of Wilcoxon rank sum test and Fisher's exact test to compare the two study groups on demographic and initial clinical variables. Randomization will be stratified by BP level at entry (at 160 systolic), and block (of 10) randomization will be done for each clinical site. We will pursue standard intention-to-treat analysis of the randomized group as a primary analysis, with the ANCOVA analyses as secondary approaches should randomization have failed on critical metrics. Blinded randomization should assure that the distribution of risk factors will not confound the associations of interest, however inclusion as covariates may reduce error variance and may therefore improve statistical power. In case of missing data, appropriate data analytic techniques will be used, which may include deletion, imputation, inclusion of an indicator of missing values, or pattern-mixture modeling. All analyses for the primary aims will use an intention-to-treat approach. Sensitivity analyses will consider the importance of missing data or loss-to-follow-up (last observation carried forward, vs. imputation of data from other sources such as clinic visits). Outcomes will be analyzed using open source statistical software R.65

For ambulatory blood pressure data, each individual 24-hour BP reading will be assessed for adequacy (defined as at least 14 daytime and 7 nighttime readings) and transformed into summary variables (e.g. 24-hour mean blood pressures). Home blood pressure data will be recorded in 2 ways: (1) the internal memory of the home BP device will be downloaded directly at the time of 6- and 12-month visits and (2) in the event of a memory failure, the participants' log book records will be reviewed and values entered. Questionnaire data will be entered and encoded along appropriate scales and scores on these questionnaires will be examined in univariate analyses to determine response distributions and coding.

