Hypothesis 1a (primary hypothesis): Improvement in systolic blood pressure measured at clinic from baseline to 12 month will be greater in the intervention vs. the usual care group. The primary outcome is the absolute change of systolic blood pressure (SBP) measured in mmHg from the study clinic randomization visit to the month 12 visit. The primary statistical test for comparison for continuous outcomes is a simple t-test across the two randomized groups. As a secondary analysis, in case of issues with randomization for differences in baseline BP, an Analysis of Covariance (ANCOVA) model with intervention group as a main effect and baseline SBP as a covariate will be fitted to study the group difference in change of SBP from baseline to week 12. Baseline sociodemographic and other clinically important characteristics at baseline will be assessed for imbalance between the two study groups and their association with the outcome using a univariate analysis (Wilcoxon rank-sum test, Kruskal-

Wallis test, Spearman correlation coefficient or Fisher's exact test). These variables will be included as covariates in the ANCOVA model if found to be moderately associated (p < 0.15) with the outcome or unbalanced (p < 0.10) between groups. Purposeful model selection method⁶⁶ will be used to select the main effects in the final model, all covariates that are significant at p < 0.10 will be kept in the final model. To assess the difference in the effect of patient characteristics on the outcome between intervention and control group, we will study the interaction between treatment and patient characteristics in the final model, as appropriate. Prespecified interactions will include analyses of effects in, older vs. younger participants (< 65), , African-American vs. other races, and initial BP level (> 160 vs. lower), and educational level (less than high school degree or more). We recognize the possibility of chance findings due to multiple comparisons by these strata, P-values for interaction will be evaluated conservatively, and data will be conservatively interpreted. If numbers in any of these subgroups are too small to allow a reasonable investigation, the subgroup analysis will be dropped. Forest plots will be constructed to assess whether subgroup effects are similar, in exploratory analyses.

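### The primary test is a valid but inefficient unadjusted t-test on SBP change; baseline-SBP ANCOVA should be the primary model, not a fallback for failed randomization

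*Combined protocol and SAP*

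**What the plan says.** Chapter 9, Hypothesis 1a, defines the primary outcome as the change in study-clinic SBP from the randomization visit to month 12 and names the test: "The primary statistical test for comparison for continuous outcomes is a simple t-test across the two randomized groups". The F4 section on sample size and power uses the same test.

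Baseline adjustment has second place in two passages. The data analytic plan describes intention-to-treat analysis as primary, "with the ANCOVA analyses as secondary approaches should randomization have failed on critical metrics". Hypothesis 1a names a secondary model: "in case of issues with randomization for differences in baseline BP, an Analysis of Covariance (ANCOVA) model with intervention group as a main effect". The one covariate named for it is SBP at baseline. Other baseline characteristics enter that model by p-value: "These variables will be included as covariates in the ANCOVA model if found to be moderately associated (p < 0.15) with the outcome", or if unbalanced at p < 0.10.

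The data analytic plan also says of baseline factors that their "inclusion as covariates may reduce error variance and may therefore improve statistical power".

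Randomization (Chapter 2, section 4) is "stratified by degree of hypertension at initial visit (> 160 systolic or below) and block-randomized by clinical sites". Neither factor appears in the primary test. Chapter 7 distinguishes two readings. On the primary care reading: "We will use the clinically measured blood pressure as the blood pressure used for eligibility criteria". On the outcome baseline: "The blood pressure from the research study visit on the day of randomization will serve as the baseline study visit for this trial".

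**The concern.** The plan recognizes that covariates can sharpen the comparison, then ties their use to a different question: whether randomization seems to have gone wrong. The precision gain does not depend on imbalance. It depends on how far baseline SBP predicts the change, which is the same issue in a perfectly balanced trial. An imbalance trigger therefore leaves the gain out of the primary result in most trials. The trigger is also undefined: no threshold says when a baseline SBP difference counts as a problem, because the p < 0.15 and p < 0.10 rules govern other characteristics.

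At stake is power and confidence-interval width, not validity. Where baseline predicts change, the t-test is also somewhat conservative, because its standard error ignores the stratification on SBP.

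**Working it through.** **Inputs from the F4 section:** difference 5 mm Hg, SD of change 16, two-sided alpha 0.05, 20% attrition, 200 per arm randomized, 160 per arm completing.

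**Plan's own figure.** n per arm = 2 × (1.960 + 0.842)² × 16² / 5² = 160.7, so 161. The exact t-test needs 162. At 160 per arm, exact t-test power is 79.6%, so the stated 80% with 320 completers is reproduced.

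**Why ANCOVA does not lose.** Let S0 and S1 be the SDs at baseline and month 12, and ρ their correlation.
- Var(change) = S0² + S1² − 2ρ·S0·S1
- Residual variance given baseline = S1²(1 − ρ²)
- Difference = (S0 − ρ·S1)² = S0²(1 − b)², where b = ρ·S1/S0 is the slope of month-12 on baseline SBP.

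This is never negative, and it is zero only at b = 1. Apart from a few degrees of freedom, ANCOVA matches or beats the t-test.

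**Size of the gain.** The documents give neither ρ nor the visit SDs, so these are assumptions. SD of change is held at 16. Baseline is normal (mean 147, SD 16) truncated to 130–180, which follows the screening limits in Chapter 2 and gives SD 11.9 with 23% above 160. Then residual SD = √(256 − 11.9²(1 − b)²). The simulation (5,000 trials per cell) randomized 400 in blocks of 10 within two sites and the 160 stratum, with 20% random loss. The ANCOVA contained arm, baseline, site and stratum.

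| Slope b | Implied ρ | Residual SD | SE ratio (simulated) | Power, t-test | Power, ANCOVA | Equivalent extra patients (1/ratio² − 1) |
|---|---|---|---|---|---|---|
| 1.0 | 0.60 | 16.0 | 1.00 | 79.8% | 79.7% | 0% |
| 0.7 | 0.47 | 15.6 | 0.977 | 79.7% | 81.0% | 5% |
| 0.5 | 0.37 | 14.9 | 0.931 | 80.6% | 85.1% | 15% |
| 0.3 | 0.25 | 13.7 | 0.857 | 81.2% | 90.0% | 36% |

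Implied ρ = b × 11.9 / √(b² × 11.9² + residual SD²).

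A second simulation with a narrower assumed baseline (SD 10.8) gave ANCOVA power of 80%, 84% and 88% at slopes 0.8, 0.5 and 0.3. With equal visit variances, residual SD = 16√((1 + ρ)/2), and ρ = 0.7, 0.5, 0.3 gives 14.75, 13.86, 12.90 and power 86%, 90%, 93%. The entry limits make that version optimistic.

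**Type I error** in the first simulation, slopes 1.0, 0.7, 0.5, 0.3 (Monte Carlo SE 0.3 points): t-test 5.4%, 4.8%, 4.6%, 3.5%; ANCOVA 5.2%, 4.8%, 5.2%, 5.0%.

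**How often the fallback would be reached.** The plan sets no threshold for baseline SBP, so p < 0.10 is used for illustration. If stratum and baseline use the same reading, imbalance at that level arises in 1.4% of trials without attrition and in 2–3% with 20% loss. If the stratum comes from a separate primary care reading (assumed correlation about 0.5), it arises in about 9%.

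**The case against.** The strongest reply is that nothing is broken. Test and sample size agree, and choosing between two valid prespecified tests is partly preference. The plan also claims room in its inputs: F4 calls SD 16 conservative and takes 5 mm Hg as smaller than the 5.4 and 9.2 mm Hg of the two earlier trials. At 5.4 mm Hg t-test power is 85%; at 5 mm Hg with an assumed SD of 15 it is 84%. The gain may be near zero, and the 90% figure needs a correlation of only about 0.25. With separate readings the 9% trigger rate is close to the 10% expected without stratification. Finally, the plan presupposes some fitted model, since it studies interactions in one and admits covariates associated with the outcome.

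Much of this stands. The t-test is sound, the 79.6% is power at the plan's own inputs and not a forecast, and the gain is a range that includes zero. The core point survives. Even at 9%, roughly nine trials in ten would not reach the trigger, and the outcome-association route feeds only the secondary model. No passage makes a baseline-adjusted estimate primary.

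**Conclusion.** The concern holds as an efficiency point. The primary analysis is valid but leaves unused a baseline measurement taken on everyone and the two randomization factors. At 160 completers per arm, a true difference of 5 mm Hg and SD of change 16, unconditional ANCOVA would have power between about 80% (no gain, slope 1.0) and 90% (slope 0.3), against about 80% for the t-test. Where the trial falls in that range depends on a correlation the documents do not give. Participants are selected for raised SBP, so a slope below 1 is plausible, but its size is unknown. No inflation of type I error is claimed. The change is worth making because it costs no patients and no data; the plan does not fail without it.

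**What to change.** Replace the primary-analysis text of Hypothesis 1a with:

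> The primary analysis is an ANCOVA of untransformed study-clinic SBP at month 12 on randomized arm, with baseline study-clinic SBP (continuous), site and the randomization stratum (SBP > 160 or not) as covariates, fitted regardless of observed balance. The adjusted difference is reported in mm Hg with a 95% CI. The unadjusted t-test on change is supportive.

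With baseline in the model, the arm effect is the same whether month-12 SBP or change is the response, so the declared outcome does not alter.

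Also:
- State which reading defines the > 160 stratum, and analyse the stratum as randomized. Define site as the unit used in the randomization.
- Replace p-value covariate selection with a short fixed list named now.
- Use the same model for Hypothesis 1b, with baseline 24-hour SBP as covariate. Leave Hypothesis 1c as a comparison of proportions.
- Editorial: state that the general transformation rule does not apply to the primary outcome, and change week 12 to month 12 in the ANCOVA sentence.

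Keep 400 participants. The cost is SAP wording only, dated before outcomes are analysed by arm. Every covariate is already collected at or before randomization.

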8. Safety metrics. We will assess SAEs both by active chart surveillance for ER or unscheduled clinic visits for enrolled veterans as well as by interview at the study visits. The CPRS system allows automated notifications to study physicians and staff for all patients enrolled in the study, so that admissions and ER visits can be reviewed on an ongoing basis; we will compile these quarterly. Every time a new medication is requested, a chart review by study staff will be triggered to confirm that medications are not being requested too frequently (protocol violation) in the intervention arm. Participants with significant safety violations in the intervention arm, identified either through interval contact or through log reviews at the 6 month visit, will be considered to have failed self-management and will be returned to usual care. Participant-reported side effects and adverse events will be actively collected at the 6-and 12-month visits in both groups.

Potentially study-related SAEs and all hospitalizations and major events will be reviewed locally by the study physicians. An un-blinded DSMB consisting of 3 experienced nephrologist-epidemiologists and a general internist, all working in the VA system and assisted by the study statistician, will review SAEs and in clinic BP data in both groups at the point where 100

participants reach the six-month time point, and every time an additional 100 participants reach six months. Any major interval SAEs or concerns will be communicated to the lead member of the DSMB who will have the option to ask for a full review.

9. Patient oriented metrics.

The Patient-Practitioner Orientation Scale has been used in prior hypertension studies at VA and assesses patients' preferred role orientation (patient- vs. provider-centered) in their clinical encounters.

Acceptability: Acceptability of the intervention will be measured using research study retention rates, patient satisfaction questionnaires including both quantitative and qualitative ratings, and adherence measures described below. We will assess participant satisfaction using 10 questions developed by the investigators. Similar questions have been used by [name] in other studies. (See Appendix 1). Clinicians with at least 2 intervention participants in the study will be surveyed with two simple Likert-scale questions regarding their opinion of the intervention and whether they would want future patients to use a similar plan.

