Hypothesis 1b: Improvement in systolic blood pressure measured by ABPM from baseline to 12 month will be greater in the intervention vs. the usual care group. For SBP measure by ABPM, we will take an average SBP over the 24 hour measurements as the outcome measure. The change in average SBP between baseline and month 12 will be compared between two intervention groups using similar analysis methods as we described for Hypothesis 1a.

Hypothesis 1c: The proportion of blood pressure reaching the 130/80 goal at month 12 in intervention group will be greater in the intervention vs. the usual care group. The outcome is a binary variable which measures whether the blood pressure was at goal. The Fisher's exact test will be used to compare the proportion of subjects with blood pressure reaching the individualized goal at month 12 between the intervention and the usual care arm. Multivariable logistic regression will be used to study the difference in outcome between two study groups with adjustment for baseline variables if randomization is unbalanced. Univariate analyses (Fisher's exact test, Wilcoxon rank sum test) will be used to assess the association between the baseline characteristics and the outcome first, then those variables that are moderately associated (p < 0.15) with the outcome or unbalanced (p < 0.10) between study groups will be included as potential covariates in multivariable model.

Hypothesis 2. Medication related SAEs and patient-reported outcomes will be similar in the two arms and there will be similar rates of ER visits and hospitalizations in the two arms. Descriptive statistics (mean, SD, median and range) will be used to summarize the number of medication related SAEs, patient-reported outcomes, number of unscheduled clinic visits, number of ER visits and hospitalizations over the 12-month study period. The difference in proportion of subjects with medication related SAEs, proportion of subjects unscheduled clinic visits, rates of patient-reported symptoms, proportion of subjects with ER visits and proportion of subjects with hospitalizations will be compared between two study groups using Fisher's exact test.

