Hypothesis 3: End-of-study levels of acceptability of the self-management protocol will be high. Patient self-efficacy will be higher in the self-management arm relative to the usual care arm. End-of-study acceptability scores will be reported descriptively as percentages. For self-efficacy scores and other scores measured at multiple time points, the change in outcome from baseline to month 12 will be compared between two study groups, and we will use similar analysis methods as those used for Hypothesis 1a.

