F4. Sample size and power. Power analyses were conducted for detecting the difference in mean change of SBP over 12 months between the subjects with intervention and subjects in control group (Hypothesis 1a) assuming a two-sided Type I error of 0.05 and an attrition rate of 20% at month 12, with sample size estimation based on a 2 sample t-test. Based on prior literature in hypertension, we assumed a standard deviation of individual change in BP over 1 year of 16 mm Hg (conservative estimate based on standard deviation of blood pressure measurement in multiple clinical studies,^{40,41} and similar to that seen in our pilot data in older CKD patients⁴³) and considered a difference of 5 mm Hg to be a clinically significant difference, a smaller difference than was seen in the TASMIN studies (which found differences of 5.4 and 9.2 mm Hg with similar sample sizes). With a 20% attrition rate, we need to recruit 200 participants per arm, or 400 total participants (total of 320 participants completing the study) to have 80% power to detect a minimum of 5mmHg (Cohen's effect size of 0.31) for the difference in mean change of SBP over 12 months between intervention and control groups. Data Safety Monitoring. We will, in addition to proactively collecting adverse events, hospitalizations, clinic visits and protocol violations, collect blood pressure data from participants at the six-month in-person visit as they self-monitor during the study. At the point where 100, 200, and 300 participants cross the 6-month point, the DSMB will review the accumulated information both from the in-clinic blood pressure averages as well as the log reports from the home BP cuffs in both groups. Although TASMIN investigators reported a less than 3% rate of protocol violations in the self-management participants, we are interested in tracking this in our intervention arm as well at the midpoint of the study. Inappropriate requests for study prescriptions will be tabulated. DSMB members will be able to examine whether out-of-range readings led to appropriate participant behavior. If this rate is considered to be too high by the DSMB, they will have the option of halting the study due to safety concerns. They will also have the option of halting the study due to SAEs or other concerns.

Chapter 10. Data Security and database management

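### Hypothesis 2 predicts similar safety, but its event outcomes get only a test for a difference, with no margin or confidence interval, so a non-significant result cannot support it

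*Combined protocol and SAP*

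**What the plan says.** Hypothesis 2 (Chapter 9, section 2, Data analytic plan) is a prediction of similarity: "Medication related SAEs and patient-reported outcomes will be similar in the two arms and there will be similar rates of ER visits and hospitalizations". Two analyses follow. The first is descriptive: "Descriptive statistics (mean, SD, median and range) will be used to summarize the number of medication related SAEs", along with the other counts. The second is inferential. The proportions with medication-related SAEs, unscheduled visits and ER visits, and the rates of patient-reported symptoms, are compared in the same way as the last item on the list: "proportion of subjects with hospitalizations will be compared between two study groups using Fisher's exact test".

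Under Hypothesis 3, for self-efficacy and "other scores measured at multiple time points, the change in outcome from baseline to month 12 will be compared between two study groups", using the Hypothesis 1a methods. Those are a t-test with ANCOVA as back-up, which again test for a difference.

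The section on sample size and power (F4) covers one outcome: "Power analyses were conducted for detecting the difference in mean change of SBP over 12 months".

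On data sources, Chapter 2, section 8 (Safety metrics) describes chart surveillance: "The CPRS system allows automated notifications to study physicians and staff for all patients enrolled in the study". It adds: "Participant-reported side effects and adverse events will be actively collected at the 6-and 12-month visits in both groups".

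**The concern.** Hypotheses 1a to 1c predict a greater improvement with self-management, so tests of a difference suit them. Hypothesis 2 predicts the opposite kind of result but is given the same kind of test. Failing to reject equality does not show equality. It may only mean that events were few.

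Nothing else in the documents fills the gap. No margin, no definition of 'similar' and no between-arm safety interval appears. The only confidence intervals are the cited blood pressure results of the two earlier UK trials (Chapter 1). The DSMB provisions (Chapter 2, section 8; Chapter 8; F4) set no numerical criterion for similarity.

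The safety of self-titration relative to usual care is a stated hypothesis of the trial. As planned, the report would give arm proportions and a p-value without saying how large an excess remains compatible with the data. That matters most for uncommon outcomes such as SAEs.

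**Working it through.** **Inputs from the documents.** F4 gives 200 per arm randomized, 320 completers in total (320/2 = 160 per arm), two-sided alpha 0.05, SD 16 mm Hg and a difference of 5 mm Hg. Chapter 2, section 4 gives 1:1 allocation.

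**Assumed.** No event rates are given, so the control risks and the doubling are assumptions. The plan defines no safety denominators, so results are shown for both 160 per arm (outcomes that depend on attending visits) and 200 per arm (chart-based events in everyone randomized).

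**1. The plan's own calculation.** n per arm = 2(1.960 + 0.842)² × 16²/5² = 161. Dividing by 0.8 for attrition gives 202 per arm. Power at 160 per arm is 79.8% (79.6% by the exact t-test). The stated 160, 400 and 80% therefore reproduce. This calculation is for blood pressure only.

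**2. Power of Fisher's test for a doubled risk.** For control risk p and intervention risk 2p, sum the product of the two binomial probabilities over all tables with two-sided Fisher p ≤ 0.05.

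| Control to intervention risk | 160 per arm | 200 per arm |
|---|---|---|
| 2% to 4% | 10% | 13% |
| 3% to 6% | 17% | 23% |
| 5% to 10% | 32% | 41% |
| 10% to 20% | 66% | 77% |
| 15% to 30% | 88% | 94% |
| 20% to 40% | 97% | 99% |

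Power falls below 50% only for control risks under about 7.5% (160 per arm) or 6.1% (200 per arm).

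**3. What a non-significant result leaves open.** With d the difference (self-management minus usual care) and (l, u) the Wilson limits in each arm (1 = self-management, 2 = usual care), the Newcombe limits are

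- lower: d − √[(p₁ − l₁)² + (u₂ − p₂)²]
- upper: d + √[(u₁ − p₁)² + (p₂ − l₂)²]

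Example: 6/200 on usual care and 12/200 on self-management, so d = 0.030. The Wilson limits are 0.0138 to 0.0639 and 0.0347 to 0.1019.

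- lower: 0.030 − √(0.0253² + 0.0339²) = −0.012
- upper: 0.030 + √(0.0419² + 0.0162²) = +0.075

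| Events, usual care vs self-management | Per arm | Fisher p | 95% interval, points |
|---|---|---|---|
| 6 vs 6 | 200 | 1.0 | −3.8 to +3.8 |
| 6 vs 12 | 200 | 0.23 | −1.2 to +7.5 |
| 10 vs 20 | 200 | 0.086 | −0.2 to +10.4 |
| 6 vs 6 | 160 | 1.0 | −4.7 to +4.7 |
| 6 vs 12 | 160 | 0.22 | −1.5 to +9.3 |
| 10 vs 20 | 160 | 0.083 | −0.2 to +12.9 |

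An observed doubling is non-significant in all four of the unequal examples.

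**4. If the arms are truly equal.** This is the probability, by enumeration, that the upper Newcombe limit exceeds the control risk, so that a doubling is not excluded.

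| True risk in both arms | 160 per arm | 200 per arm |
|---|---|---|
| 3% | 73% | 64% |
| 5% | 51% | 41% |
| 10% | 17% | 10% |
| 15% | 3.8% | 1.4% |
| 20% | 0.6% | 0.1% |

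**The case against.** The strongest reply has four parts.

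- **The misreading is hypothetical.** The plan never says that p>0.05 will be taken as similarity, and anyone with the counts and denominators can compute an interval. Both points are true. But the plan then offers no inferential basis at all for Hypothesis 2, and leaving the measure and the threshold until after the data are seen is what pre-specification is meant to prevent.
- **The size rests on assumed event rates.** At control risks of 15% or more the power problem largely disappears, and nothing in the documents shows that unscheduled visits, ER visits or symptoms are rarer than that. This stands. It confines the power concern to uncommon outcomes. It does not repair the mismatch between hypothesis and test, which holds at any event rate.
- **Some links are inferred.** The sentence on scores sits under Hypothesis 3, and the scales repeated at month 12 are not obviously safety measures. SAEs come from both charts and interviews, so the choice between 160 and 200 is not settled by the plan. Both points are fair. The scores are a minor part of the concern, and the conclusion is the same at either denominator.
- **The DSMB covers safety.** It can halt the trial and so protects participants while it runs. It does not supply a final between-arm estimate.

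**Conclusion.** The concern holds. Hypothesis 2 asserts similarity, and the analysis named for its event outcomes can only produce evidence against it. For an assumed control risk of 5%, the trial has 32% to 41% power to detect a doubling. Even with truly equal arms it would fail to exclude a doubling 41% to 51% of the time. At 10% these become 66% to 77% and 10% to 17%, and at 20% the power problem is negligible. All of these figures depend on assumed risks, on doubling as the benchmark and on 160 to 200 per arm. The logical gap depends on none of them. This should be fixed before the final analysis. It does not affect the primary blood pressure comparison.

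**What to change.** Restate Hypothesis 2 as estimation. Suggested SAP wording:

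> For medication-related SAEs, patient-reported symptoms, unscheduled visits, ER visits and hospitalizations, the difference in the proportion of participants affected (self-management minus usual care) will be reported with a 95% Newcombe interval, which is the main safety summary. The upper limit will be described as the largest excess compatible with the data at the 95% level. A p-value above 0.05 will not be taken as evidence of similarity.

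Further points:

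- State the denominator for each outcome.
- For any patient-reported score analysed by the Hypothesis 1a methods, give the mean difference with its 95% interval.
- Fisher p-values may stay beside the intervals. Another sound risk-difference interval would serve as well as Newcombe's, provided it is named in advance.
- If 'similar' is to remain a conclusion, the study team must record the excess it would accept for each outcome before the final analysis. That figure is theirs to set.
- Optionally, add a rate ratio with a 95% interval for counts of ER visits and hospitalizations.

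The cost is SAP wording and a few table columns, with no new data and no change in sample size. The safety statement becomes less favourable, and intervals for rare SAEs will be wide. Fisher and Newcombe can disagree near the boundary: 10 vs 21 of 200 gives p = 0.060 with an interval of +0.2 to +11.0 points. That is why the plan should say which one leads.
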